2.3 Statistical Analysis

A total of up to 15 patients will be enrolled. Due to the lack of preliminary data as well as exploratory nature of the study, no sample size and power analyses were performed. We expect to screen approximately 45 patients to enroll up to 15 eligible patients into this trial.

All clinically relevant baseline and follow-up data will be tabulated. Means (SDs), medians (ranges), and 95% confidence intervals will be reported for continuous variables and frequencies, percentages, and 95% confidence intervals for categorical variables. Specifically, each of the two primary endpoints (the procedural success at 30-days and the composite binary response variable at 6-months) will be summarized using both a point estimate and its exact confidence interval based on a binomial distribution. Other binary safety and efficacy secondary endpoints will be analyzed similarly. Continuous secondary endpoints (e.g., hemodynamics data) will be reported using descriptive summary statistics as well as a point estimate and its confidence interval based on a normal distribution assumption. The changes from baseline to each follow-up timepoint will additionally be evaluated using the McNemar matched pairs test for dichotomous variables and the t-test for continuous variables. In the presence of distributional non-normality, the Wilcoxon signed rank test will be used instead of the t-test. Data transformations such as log or square-root may also be considered. The analyses of NYHA functional classification will involve comparison of the baseline and post-operative (at each timepoint) functional class and determination of the percentages of patients improving, not changing, or worsening at each postoperative timepoint. The same principle will be applied to quality of life score (KCCQ) and 6-minute walk distance. Although this is an exploratory analysis, we anticipate 50% of patients will demonstrate improvement in one of the three pre-specified components of the primary efficacy outcome.

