The time-to-event approach may be considered to analyze some of safety and efficacy endpoints (e.g., time to treatment failure, event-free survival, and overall survival) while taking censoring into account in data analyses. Such endpoints will be summarized using the Kaplan-Meier method. Confidence intervals for the medians and survival rates at different time points will be constructed, when appropriate. For a continuous endpoint measured repeatedly over time, a mixed-effects regression model may be employed to study its over-time trajectory or change patterns. All these results will be reported descriptively.

The intent-to-treat approach will be used for data analyses of this trial. That means all enrolled patients will be included in the interim and final data analyses regardless of their eligibility or subsequent events. Patients who are lost to follow-up or drop out of study prior to their scheduled follow-up evaluation time due to any reason will be treated as a treatment failure for response determination and censored for time-to-event type of endpoints at the time of their last follow-up if no relevant event has occurred by then. A secondary analysis that includes only all eligible patients may be conducted in addition to the primary analysis described above at the discretion of the trial PI and study biostatistician. However, such analysis may not serve as the basis for drawing conclusions concerning treatment safety or efficacy, and the reasons for excluding patients from the analysis should be clearly reported.

All enrolled patients will be evaluable for adverse events from the time of their protocol treatment. Adverse events will be tabulated by type and severity according to the NCI Common Terminology Criteria for Adverse Events (CTCAE) version 4.0.

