During the entire study period, adverse events will be closely monitored by the trial PI and clinical trial coordinator of this study, working along with the study DSMB. In particular, formal stopping rules on the 6-month mortality are stipulated in this protocol (please refer to section 4.1 “Efforts to minimize procedure risks”). In addition, in the event that other adverse events (e.g., surgical complications) are thought to be excessive for the study patient population at any point of the trial, the patient accrual to the trial will be suspended immediately, pending a review of all adverse events data. A final decision will be made by the trial PI and DSMB as to whether the trial should be amended, terminated or continue accrual. Such decision should be filed with and pre-approved by the institutional IRB.

2.4 Study Endpoints:

The primary safety endpoint is procedural success at 30-days. Procedural success will include:

- Successful vascular access without unplanned major vascular complication as defined by VARC-2, delivery and retrieval of the transcatheter valve delivery system, correct position of both the vascular stent(s) and transcatheter valve in the IVC, a single valve placed within the IVC, and no need for additional surgery or re-intervention (including drainage of pericardial effusion) with the patient being alive at 30-days.

The primary efficacy endpoint will be improvement in one of three variables assessed from baseline to 6-months.

- Improvement of KCCQ score >15. This has been shown to correlate with improvement in quality of life with heart failure patients²².
- Improvement in 6-minute walk test (6MWT)>70 meters. This has been shown to provide prognostic information in patients with congestive heart failure after an intervention²³.
- Improvement of greater than 6% of peak Vo2 in cardiopulmonary exercise testing. In a heart failure population, this has been shown to help assess prognosis in patients who were instituted in an exercise program ²⁴.

Secondary endpoints will be evaluated at several timepoints and will be divided into safety and efficacy: The first in the acute setting which will be out to 30 days or hospital discharge whichever being longer; additional time points will be at midterm (6 months post-procedure), long term (1 year and annually up to 5-years post-procedurally.)

Secondary safety endpoints include:

- All stroke and TIA (VARC-2)
- Mortality (VARC-2)
- Myocardial infarction (VARC-2)

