- Acute Kidney Injury (VARC-2)
- Major Vascular Complication (VARC-2)

Secondary efficacy endpoints include:

- Assessment of improvement of LE edema by the Villalta Score²⁵. A 3.1 point improvement in this scale was associated with improved quality of life²⁶.

Besides the above formal secondary endpoints, we will monitor for the following throughout the trial:

- Deep Vein/IVC thrombosis or pulmonary embolism
- Improvement in grades of tricuspid regurgitation as assessed by echocardiogram
- Changes in TAPSE by echocardiogram for RV function
- Pleural effusions
- Additional quality questionnaires to assess for changes in ascites (EORTC QLQ-C30²⁷ and ESAS-AM²⁸). A 10-point change in mean score in the QLQ-C30 has been shown to be a meaningful response (O'Connor R. Measuring Quality of Life in Health Churchill Livingstone: Philadelphia; 2004). A decrease of 1.25 points in the ESAS-AM has been shown to correlate with symptom improvement after paracentesis²⁸.

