4.0 RISK AND BENEFIT ANALYSIS

There are potential risks associated with transcatheter heart valve implantation. There are risks related to the overall procedures (complications associated with standard cardiac catheterization which include bleeding, infection, stroke, death, cardiac arrest, pacemaker implantation, allergic reactions, emergency open heart surgery, and emergency blood transfusion, prolonged hospital stay, renal failure, groin lymphocele, limb ischemia, myocardial infarction, injury to adjacent structures including nerves, blood vessels, or other structures.) In addition, there are also risks associated with the valve itself which include valve embolization and/or migration and the emergent need for open heart surgery and possibly death, as well as valve thrombosis which can lead to death, stroke, pulmonary embolism, or venous thrombosis. Structural valve deterioration may also occur in the form of wear, fracture, calcification, leaflet tear/tearing from the stent posts, leaflet retraction, suture line disruption of components of a prosthetic valve, thickening, stenosis.

There are risks associated with stenting of the IVC for valve implantation. These include migration of the stent and injury to the vessels of the heart or the heart itself, as well as venous thrombosis and stroke. Although these risks are present, the potential of a new therapy which improves the quality of life in those patients who are otherwise ineligible for surgery outweighs these potential risks.

Pleural effusions may occur either immediately post-operatively, or at follow up. It is recommended that a trial of diuretic therapy, as well as attempts at diagnosis of the effusion (exudative vs. transudative) be attempted if the patient becomes symptomatic. If diuretic therapy fails, a thoracentesis should be considered for symptomatic relief. If the effusion reoccurs, additional thoracenteses may be considered. Alternatively, the placement of a permanent drainage catheter, or pleuredesis may be another option in patients with continued fluid accumulation who remain symptomatic.

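### The 6-month efficacy response has no rule for a repeat caval or tricuspid procedure, so a patient who improves after one is scored as a responder to the caval valve

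*Combined protocol and SAP*

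**What the plan says.** Section 2.3 sets the analysis population: "all enrolled patients will be included in the interim and final data analyses regardless of their eligibility or subsequent events". It then gives one rule that turns a patient into a failure for response: leaving the study or being lost before the scheduled assessment.

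Section 2.4 defines the outcome: "The primary efficacy endpoint will be improvement in one of three variables assessed from baseline to 6-months". The thresholds are a KCCQ gain above 15, a 6-minute walk gain above 70 m, or a peak VO2 gain above 6%. Nothing is said about treatment received between the index procedure and the tests.

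The primary safety endpoint in 2.4 does count further surgery or repeat intervention as failure, but only to 30 days. Section 2.3 also names time to treatment failure as a possible endpoint, without defining it.

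On fluid drainage, inclusion criterion 2 requires ascites at entry. Section 4.0 says of pleural effusions: "If diuretic therapy fails, a thoracentesis should be considered for symptomatic relief", and goes on to repeat drainage, a permanent catheter or pleurodesis. Section 2.4 remarks: "A decrease of 1.25 points in the ESAS-AM has been shown to correlate with symptom improvement after paracentesis". The assessment lists in section 5 and Table 1 record diuretics but have no item for paracentesis or thoracentesis.

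On size and analysis, section 2.3 says: "A total of up to 15 patients will be enrolled"; "no sample size and power analyses were performed"; "we anticipate 50% of patients will demonstrate improvement in one of the three pre-specified components of the primary efficacy outcome". Each primary endpoint is to be "summarized using both a point estimate and its exact confidence interval based on a binomial distribution".

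**The concern.** Objective 2 asks what the caval valve does for symptoms of right heart congestion. If the valve or stent fails, a further procedure is done, and the patient then feels better, the plan's rule credits that improvement to the index valve. In a randomised trial the same rule would at least apply to both arms. Here there is no comparator, so the response rate absorbs the effect of the later treatment and nothing in the analysis can remove it.

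Section 4.0 makes such events foreseeable: it lists valve embolization or migration, valve thrombosis and stent migration among the risks. The safety endpoint shows that the plan regards re-intervention as a failure of the procedure, yet no matching rule carries into the efficacy endpoint.

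Drainage is a related but separate matter. It may change how a patient feels on the day of testing, and the plan neither dates it in the visible schedule nor relates it to either set of tests.

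**Working it through.** **Step 1. Apply the rules as written.** Take a patient who attends the 6-month visit and passes one threshold, or who leaves the study:

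| Event after the index procedure | 30-day safety endpoint | 6-month efficacy endpoint |
|---|---|---|
| Re-intervention on stent or valve within 30 days | Failure | Responder |
| Re-intervention, or another caval or tricuspid procedure, after 30 days and before the 6-month tests | Not affected | Responder |
| Lost to follow-up or drop-out before 6 months | Depends on timing | Failure |

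The responder entries follow from three things together: everyone is analysed, the endpoint is unconditional, and no other failure rule exists. The plan does not state them outright.

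**Step 2. The plan's own figure.** The only number attached to the efficacy endpoint is the anticipated 50%. It has no derivation, so there is nothing to reproduce. At n = 15 it equals 0.50 × 15 = 7.5 patients, so the nearest possible results are 7/15 and 8/15.

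**Step 3. Weight of one patient.** 1/15 = 0.067, or 6.7 percentage points. With fewer than 15 enrolled, each patient weighs more.

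**Step 4. The planned analysis with patients reclassified.** The exact (Clopper-Pearson) interval for x responders of n runs from the 0.025 quantile of Beta(x, n − x + 1) to the 0.975 quantile of Beta(x + 1, n − x). The 95% level is taken from the general sentence on categorical variables in section 2.3. The starting count of 8 and the numbers reclassified are assumptions, because the documents give no event frequency.

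| Responders reclassified (assumed) | Rate | Exact 95% CI |
|---|---|---|
| 0 | 8/15 = 53.3% | 26.6% to 78.7% |
| 1 | 7/15 = 46.7% | 21.3% to 73.4% |
| 2 | 6/15 = 40.0% | 16.3% to 67.7% |
| 3 | 5/15 = 33.3% | 11.8% to 61.6% |

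Across 0 to 3 patients the shift is 0 to 3 × 6.7 = 20 points. In this example one patient takes the estimate from above to below the anticipated 50%.

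**Step 5. Direction of drainage.** Response is the 6-month value minus the baseline value, compared with a threshold. If drainage shortly before the 6-month tests improves the first value, it favours the device. If drainage shortly before the baseline tests improves the second, it works against the device. Section 5.1 allows baseline KCCQ up to 21 days, and the walk and exercise tests up to 90 days, before the procedure; Table 1 allows ±14 days at 6 months. None of these windows refers to drainage, so the direction of any net bias cannot be settled from the documents.

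**The case against.** **The analysis-set sentence only says who is included.** True. Keeping every enrolled patient in the analysis is not an error, and a reader should not infer that this sentence scores anyone a responder. The gap lies in the scoring rule, which is silent on intervening procedures.

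**Surgical rescue is remote.** A reader might infer that tricuspid surgery is the main problem. The documents do not support that: inclusion criterion 4 requires that operation be precluded, and exclusion 1 removes operable patients. Re-intervention on the stent or valve, or another catheter procedure, is the more plausible route. A re-intervention within 30 days would also show up in the safety endpoint, though it would not change the efficacy score.

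**As-observed scoring is a legitimate strategy.** It is, if it is declared and interpreted as the outcome of valve plus whatever followed. It is not declared, and it does not match the stated objective.

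**The study is exploratory, with no efficacy threshold.** This stands, and it limits the consequence. The shifts above sit inside an interval about 52 points wide (78.7 − 26.6). Nor is the response rate the only efficacy information: the Villalta score, NYHA class, changes in KCCQ and walk distance, echocardiographic measures and 6-month right heart catheterization are also collected. It is, however, the named primary efficacy endpoint.

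**The drainage evidence is indirect.** A reader might infer that drainage is shown to produce responders. It is not: the remark in 2.4 concerns the ESAS-AM, which is no part of the primary endpoint, and no figure links drainage to KCCQ, walk distance or peak VO2. Relieving an effusion that arose after implant may only return the patient towards baseline.

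**Drainage may be captured elsewhere.** Section 8.1 places the case report forms in an addendum that is not included. Pleural effusions are monitored, and events are assessed at each post-procedure visit. What can be said is that the visible schedule has no item for drainage, and that section 7.1 does not treat stable symptoms of existing disease as adverse events.

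**Conclusion.** The point holds for intervening procedures. Following the plan exactly would credit improvement after a repeat caval or tricuspid procedure to the index valve, with no control arm to correct it. This is more than a missing detail, because the rule as written produces a definite and wrong attribution.

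The size is 6.7 points per patient at n = 15. The total rests on an assumed 0 to 3 affected responders, giving 0 to 20 points. No figure in the plan is contradicted.

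For drainage the conclusion is weaker. Its timing should be recorded and its influence examined, but the documents do not show that it creates responders, and the bias can run against the device as well as for it.

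**What to change.** In sections 2.3 and 2.4, state that a patient is a non-responder in the primary efficacy analysis if any of the following occurs between the index procedure and the 6-month tests: tricuspid surgery, any further transcatheter tricuspid or caval procedure, device removal, mechanical support, or transplant. Report the as-observed rate, with its exact interval, as a sensitivity analysis.

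Add a case report form line for the date of each paracentesis and thoracentesis, covering the period before the baseline tests as well as follow-up. Report drainages before both sets of tests descriptively. Add one sensitivity analysis that uses a short window before the tests, with its length and handling fixed before any 6-month results are seen. A long window would penalise patients drained well before testing.

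These changes concern classification and recording only; they leave patient care unchanged. The cost is a few sentences of protocol text, one form line and two sensitivity analyses. The downside for the sponsor is that the primary response rate can only stay the same or fall.

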7.2 Serious Adverse Events

A serious adverse event (SAE) is any untoward medical occurrence that:

- results in death
- is life-threatening, i.e., an event that, in the view of the investigator, places the subject at immediate risk of death from the event as it occurred (it does not include an event that could have caused death if it had been more severe)
- requires inpatient hospitalization or prolongs the existing hospitalization
- results in persistent or significant disability or incapacity, where disability is defined as a substantial disruption of a person's ability to conduct normal life functions, either reported or defined as per clinical judgment
- is a congenital anomaly or birth defect (if exposure to product just before conception or during pregnancy resulted in an adverse outcome in the child)

All investigators will be responsible for reporting serious adverse events to the sponsor and their reviewing IRBs in accordance with local guidelines. In addition, all SAEs will be reviewed by an independent Data Safety Monitoring Board (DSMB) in accordance with their charter. (An SAE will be reported to the Sponsor and DSMB Chair within 24 hours from when the event was discovered and the SAE CRF will be submitted no later than ten (10) days after the SAE was discovered) Study device causality for SAE's will be graded as unlikely, possible or probably.

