8.0 DATA MONITORING AND QUALITY CONTROL

8.1 Case Report Forms (CRFs)

Case report forms (CRFs, see addendum) will be generated, based on the investigational plan. An electronic clinical trial management system (RedCap, Vanderbilt U, TN) will be used to collect all patient data during the trial by the data coordinators or their designee. Data will be collected in a paper form or in electronic format and entered into the electronic clinical trial management system. Paper forms will be kept in a secure location and only accessible to the data coordinator or investigator.

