		____/____ ____:____ — ____:____	 1 Ongoing  2 Resolved  3 Pt. Died	____/____ ____:____ — ____:____	 1 Mild  2 Moderate  3 Severe  4 SAE*	 0 NO  1 YES**	 0 NO  1 Stopped temporarily  2 Stopped Permanently	 1 Unlikely  2 Possibly  3 Probably	
		____/____ ____:____ — ____:____	 1 Ongoing  2 Resolved  3 Pt. Died	____/____ ____:____ — ____:____	 1 Mild  2 Moderate  3 Severe  4 SAE*	 0 NO  1 YES**	 0 NO  1 Stopped temporarily  2 Stopped Permanently	 1 Unlikely  2 Possibly  3 Probably	
		____/____ ____:____ — ____:____	 1 Ongoing  2 Resolved  3 Pt. Died	____/____ ____:____ — ____:____	 1 Mild  2 Moderate  3 Severe  4 SAE*	 0 NO  1 YES**	 0 NO  1 Stopped temporarily  2 Stopped Permanently	 1 Unlikely  2 Possibly  3 Probably	

Describe:
 <hr/> 
If event is SAE then submit AE form to medical reviewer within 24 hours. **If YES and device related, complete UADE form
									

UNANTICIPATED ADVERSE DEVICE EFFECT FORM

1. Date form completed		— / — / — —	MO	DAY	4-Digit YEAR			
2. Date and time of onset:		— / — / — —	MO	DAY	4-Digit YEAR	— : —	(Military time)	
3. Has event resolved?  YES  NO		If YES, Date/Time resolved: — / — / — —						
		MO	DAY	4-Digit YEAR	— : —	(Military time)		
4. Relationship to study device: (choose one)		 NOT related	 Probably related	 Unknown				

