		 Possibly related	 Definitely related					
If related, (1, 2 or 3) then specify Serial ID# for device _____								
5. In your opinion, is this a UADE*  YES  NO								
6. Action taken (Check all that apply)		 YES  NO None						
		 YES  NO Medication, specify: _____						
		 YES  NO Surgery, specify _____						
		 YES  NO Other, specify _____						
7. Severity (Check one)		 Mild  Moderate  Severe  Life threatening						
8. Outcome (Check all that apply)								
YES	NO			YES	NO			
		A. Continuing WITHOUT treatment				E. Recovered WITHOUT treatment		
		B. Continuing WITH treatment				F. Recovered WITH treatment		
		C. Continuing with sequelae, specify: _____				G. Patient expired (attach copy of autopsy or death summary)		
		D. Temporary disability				H. Permanent disability		
9. Description of adverse effect: _____								
* An Unanticipated Adverse Device Effect (UADE) is any serious adverse effect on health or safety, or any life-threatening problem or death caused by or associated with this device, if that effect, problem, or death is not identified in nature, severity, or degree of incidence in this Investigational Study; or any other unanticipated serious problem associated with this device that relates to the rights, safety or welfare of the subjects. UADEs must be reported to the principal investigator and the IRB within 10 working days.								
I verify that the form completed for this UADE is accurate and representative of the data available in source documentation.								
Investigator's signature				Date — / — / — — MO DAY 4-Digit YEAR				

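### The AE form mixes seriousness with intensity and holds no CTCAE grade, so the severity table planned in section 2.3 cannot be built from that form alone

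*Combined protocol and SAP*

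**What the plan says.** Section 2.3 (Statistical Analysis) makes one commitment for general adverse events: "Adverse events will be tabulated by type and severity according to the NCI Common Terminology Criteria for Adverse Events (CTCAE) version 4.0". In the text available, CTCAE otherwise appears only in the list of abbreviations. No section asks a site, reviewer or committee to assign a CTCAE grade.

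Section 7.2 defines a serious adverse event by five criteria: death, threat to life, hospitalization, disability and congenital anomaly. Two of them read "requires inpatient hospitalization or prolongs the existing hospitalization" and "is life-threatening, i.e., an event that, in the view of the investigator, places the subject at immediate risk of death". Each SAE goes to the sponsor and the DSMB chair within 24 hours, and "the SAE CRF will be submitted no later than ten (10) days after the SAE was discovered".

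The Adverse Event Form, printed after the References, has one *Intensity* column coded 1 Mild, 2 Moderate, 3 Severe, 4 SAE. Its footnote reads: "If event is SAE then submit AE form to medical reviewer within 24 hours". A separate *Outcome* column includes a box for death.

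Item 7 of the Unanticipated Adverse Device Effect (UADE) Form uses a different scale (Mild, Moderate, Severe, Life threatening) and asks for one box to be checked.

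On the forms in general, section 8.1 says: "Case report forms (CRFs, see addendum) will be generated, based on the investigational plan". That addendum is not among the documents available.

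**The concern.** Severity and seriousness are separate attributes. A moderate event that lengthens a hospital stay is serious under section 7.2. A severe event may meet none of the section 7.2 criteria. Placing SAE as a fourth step above Severe puts both attributes on one scale, and a single tick can then record only one of them.

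Short-term safety is the first study objective in the Protocol Summary. Section 2.3 also provides that accrual is suspended if other adverse events are thought excessive, pending review of all adverse event data by the trial PI and the DSMB. A tabulation that separates grave from minor serious events would support that review. With at most 15 patients, each event weighs heavily in any table.

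**Working it through.** No figure in the plan bears on this point, so there is nothing to recompute. The check sets the planned table against the fields that would feed it.

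**What the table needs:** event type, and a CTCAE v4.0 severity, for every event (section 2.3).

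**What the AE form supplies:** a free-text description, one intensity code (1 to 4), an outcome (ongoing, resolved, died), expectedness, whether treatment was stopped, and device causality. It has no CTCAE grade, no serious yes/no item, and no field for the section 7.2 criterion that was met.

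**Case by case, if one intensity box is ticked:**

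| Event | Severity on the AE form | Seriousness on the AE form |
|---|---|---|
| Non-serious | Mild, Moderate or Severe, but not a CTCAE grade | Implied by the absence of code 4 |
| Fatal | Identifiable from the outcome column | Identifiable from the outcome column |
| Non-fatal SAE, coded 4 | None | Flagged, criterion not recorded |
| Non-fatal SAE, coded 1 to 3 | Mild, Moderate or Severe | No flag |

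The third row is the gap in the severity table. Within code 4, no coded field separates a life-threatening event from a prolonged stay. The fourth row avoids that gap by dropping the seriousness flag.

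**An example from the protocol.** The radiation precautions in section 5.2.1 require a reported KAP between 150 and 250 Gy/cm² to be entered as a serious adverse event. That is a dose threshold and implies no clinical intensity. On the AE form it would take the same code 4 as a non-fatal life-threatening complication.

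**Other sources of severity in the documents:**

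1. *UADE form.* Item 7 includes a life-threatening level, but only a subset of events gets this form. Its trigger, "If YES and device related, complete UADE form", is attached to the YES box of the *Expected Event?* column, which does not fit a form for unanticipated effects. It is not a dependable back-up.
2. *SAE CRF.* Section 7.2 names it, but its fields are not shown. It may or may not hold a grade. The table of contents lists only the AE and UADE forms, and the AE form's footnote makes that form the 24-hour SAE notice.
3. *Two ticks on the AE form.* The intensity column carries no instruction to check one box, unlike item 7 of the UADE form, so ticking Moderate and SAE together is not ruled out. Nothing instructs sites to do so, and the life-threatening level would still be missing.
4. *Later grading from narratives.* This is possible from the description fields and from the supporting documentation that section 8.4 requires for SAEs. No such step is described.

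**The case against.** The strongest reply is that the AE form is not the only record. Section 7.2 names a separate SAE CRF, section 8.1 places the CRFs in an addendum, and with at most 15 patients the serious events could be graded from source documents. This stands. It limits the point to what the AE form can supply by itself.

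A reader might infer that the planned table cannot be produced at all, or that the severity of serious events is lost for good. The documents do not support that while the SAE CRF is unseen.

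A reader might also infer that the DSMB could not tell a prolonged stay from a life-threatening event. Section 7.2 has the DSMB review all SAEs, with its chair told of each within 24 hours, and section 8.3 gives it access to all necessary safety and event data. Its members can see described events, not only codes.

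A third inference would be that expedited reporting will be missed. The 24-hour duty follows from meeting the section 7.2 criteria, not from ticking code 4, and the form's footnote likewise refers to the event being an SAE. What remains is that the form carries no other seriousness marker to check against.

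Finally, the main safety measures do not use this item. The primary safety endpoint is 30-day procedural success. The secondary safety endpoints follow VARC-2, which has its own classes in Appendix B (disabling stroke, kidney injury stages, major and minor vascular complications). The stopping rule in section 4.1.3 counts deaths. This also stands, and it sets the weight of the point.

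**Conclusion.** The point holds in limited form. Section 2.3 promises severity by CTCAE v4.0, and the AE form as shown does not collect it. For a non-fatal SAE under a single tick, the form loses either the severity or the seriousness flag, and it has no life-threatening level in any case. The planned severity table cannot be built from the AE form alone.

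The effect is limited to the descriptive AE tables and the data for AE review. No count of affected events can be given, because the documents give no expected number of SAEs.

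The conclusion assumes that one intensity box is ticked per event and that the AE form is used as printed. If the unseen SAE CRF already holds a CTCAE grade, the gap for serious events closes, but the mixed scale on the AE form and its lack of a grade for other events remain. The finding rests on the mismatch inside the documents, which do not reproduce the CTCAE grade definitions. It should be corrected because the correction is cheap, not because it threatens the trial's main conclusions.

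**What to change.** 1. On the AE form, replace the Intensity item with a CTCAE v4.0 grade, required for every event.
2. Add a separate *Serious: yes/no* item with the section 7.2 criterion that was met, and attach the 24-hour footnote to that item. Provide an entry for events that the protocol designates as serious, such as the radiation threshold in section 5.2.1, because none of the five criteria need apply to them.
3. Use the same severity scale on the AE, SAE and UADE forms. If the SAE CRF already records a grade, say so in section 2.3 and name it as the source.
4. In section 2.3, state that severity and seriousness are tabulated separately and who assigns the grade.
5. While the forms are open, reconcile the UADE trigger with the *Expected Event?* column.

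The cost is edits to the forms, the matching REDCap fields and a sentence or two in section 2.3. No visits or tests are added.
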